**5.3.8 Subgroup Analyses**

Time to confirmed perceptible relief will be analyzed based on the following subgroups: age group (<18 years, ≥18 years), gender, race (white, non-white) and baseline categorical pain (moderate, severe). The survival function and the median survival time will be estimated by the Kaplan-Meier method within each subgroup.

**5.4 DEMOGRAPHIC AND BASELINE CHARACTERISTICS**

Baseline and demographic characteristics will be presented by treatment group for each analysis set. For continuous variables, descriptive summaries will include number of subjects, mean, standard deviation, median and range (min, max). For categorical variables, the number and percent of subjects in each response category will be presented.

**5.5 PREVIOUS AND CONCOMITANT MEDICATIONS**

Previous and concomitant medications will be coded. Previous medications will be those that were discontinued before the surgery day. Concomitant medications will be those continued through, or started on, the surgery day and up through the 12-hour assessment period. In addition, those medications taken after the 12-hour assessment period through the follow-up interview for an AE will be considered concomitant medications. Medications taken after the 12-hour assessment through the follow-up call that were not taken for an AE will not be collected on the CRF or summarized.

Previous medications and concomitant medications will be summarized by treatment in separate tables. Number and percentage of subjects receiving each coded medication will

be presented by treatment. Additionally, concomitant medications taken by greater than or equal to 5% of subjects in at least one treatment group will be presented.

## **5.6 SAFETY ANALYSIS**

### **5.6.1 Adverse Events**

Treatment-emergent AEs are those with a start date and time at or after the time of study drug administration. All summaries described below are for treatment-emergent AEs except where noted. Non-treatment-emergent AEs will be provided in a listing.

The number and percentage of subjects experiencing AEs will be tabulated by treatment, system organ class and preferred term using the MedDRA coding dictionary. The number and percentage of subjects experiencing treatment-related AEs will also be presented by system organ class and preferred term. Treatment-related AEs will include events marked as being at least possibly related to study treatment. The number and percentage of subjects with AEs will be presented by severity. Subjects will be counted only once for each system organ class and preferred term by selecting the most severe event.

The number of subjects with the most commonly reported adverse events (those reported by 5% or more in any one treatment group) will be summarized by treatment, system organ class and preferred term. The number of subjects with adverse events will also be summarized by demographic characteristics: age group (<18 years, ≥18 years), gender, and race.

The number and percentage of subjects experiencing SAEs or who discontinued the study due to an AE will be presented by system organ class and preferred term. These displays will include all AEs, not just treatment-emergent AEs.

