### 12.2. Safety Assessments

Safety will be monitored via AE reporting. If an AE is reported, the subject will be asked to elaborate on the nature of the event. The investigator or designated study staff will evaluate and record according to the AE Reporting section of the protocol.

Normal consequences of dental surgery (e.g., pain, swelling, bruising) are not considered AEs unless the investigator believes the condition worsened or was aggravated following study drug therapy.

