### **13.1. Definitions**

#### **13.1.1. Definition of Adverse Event**

An AE is any untoward medical occurrence that occurs in a subject after they have signed an informed consent for a study. The event does not need to have a suspected causal relationship with the IP. Therefore, an AE can be any unfavorable and unintended sign, symptom, disease or injury temporally associated with the subject's participation in the study. Examples of AEs include, but are not limited to:

- Abnormal test findings,
- Clinically important signs and symptoms,
- Changes in physical examination findings,
- Hypersensitivity, and
- Progression/worsening of underlying disease.

Additionally, they may include the signs or symptoms resulting from:

- Overdose,
- Withdrawal,
- Abuse,
- Drug misuse,
- Drug interactions,
- Medication errors,
- Product dependency,
- Exposure *in utero*, and
- Study related procedure

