### **13.2.2. Causality Assessment**

The medically qualified Investigator's assessment of causality to IP (i.e., relationship to IP) must be provided for all AEs (serious and non-serious). The causality assessment is the determination of whether there exists a reasonable possibility that the IP caused or contributed to an AE.

- Not Related - An AE that is not related to the use of the drug
- Doubtful - An AE for which an alternative explanation is more likely, e.g., concomitant drug(s), concomitant disease(s), or the relationship in time suggests that a causal relationship to IP is unlikely.
- Possible - An AE that might be due to the use of the drug. An alternative explanation, e.g., concomitant drug(s), concomitant disease(s), is inconclusive. The relationship in time is reasonable; therefore, the causal relationship to IP cannot be excluded.
- Probable - An AE that might be due to the use of the drug. The relationship in time is suggestive (e.g., confirmed by dechallenge) and an alternative explanation is less likely, e.g., concomitant drug(s), concomitant disease(s).
- Very Likely - An AE that is listed as a possible adverse reaction and cannot be reasonably explained by an alternative explanation, e.g., concomitant drug(s), concomitant disease(s). The relationship in time is very suggestive (e.g., it is confirmed by dechallenge and rechallenge) for a causal relationship to the drug.

Any AE that occurs after the informed consent has been signed, until first usage of investigational product, will be considered non-treatment emergent and cannot (by virtue of time of occurrence) have a causal relationship with the IP.

If the Investigator determines an AE is associated with study procedures, the Investigator must record this suspected causal relationship in the source documents and the SAE form, as appropriate, and report such an assessment in accordance with the SAE reporting requirements, if applicable.

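### Treatment-emergent AEs are defined by start time alone, so a non-serious AE that begins before dosing and worsens afterwards drops out of the AE summary tables

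*SAP*

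**What the plan says.** SAP 5.6.1 gives the definition: "Treatment-emergent AEs are those with a start date and time at or after the time of study drug administration". Protocol 14.8.1 has the same definition, so neither document fills a gap in the other.

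SAP 5.6.1 then sets the scope of the tables: "All summaries described below are for treatment-emergent AEs except where noted". Events outside the definition are handled separately: "Non-treatment-emergent AEs will be provided in a listing" (Listing 16.2.6.2 in SAP Appendix 2). The one exception noted is for SAEs and AEs leading to discontinuation: "These displays will include all AEs, not just treatment-emergent AEs". For the related-event tables the rule is: "Treatment-related AEs will include events marked as being at least possibly related to study treatment". No exception from the treatment-emergent restriction is attached to it.

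Protocol 13.2.2 says that an AE occurring after consent and before first use of the product "will be considered non-treatment emergent and cannot (by virtue of time of occurrence) have a causal relationship with the IP".

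Two other places deal with worsening. Protocol 12.2 says that normal consequences of dental surgery, with pain, swelling and bruising as examples, "are not considered AEs unless the investigator believes the condition worsened or was aggravated following study drug therapy". Protocol 13.1.1 includes "Progression/worsening of underlying disease" among its examples of an AE.

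**The concern.** Every subject in this trial has a recorded interval between surgery and dose. Surgery may involve local anaesthetic and/or nitrous oxide (Protocol 10.8.1). Baseline pain is then scored up to 4.5 hours after the last stitch, dosing follows within 5 minutes (Protocol 10.3), and AEs are collected from consent onwards (Protocol 13.3.1). An event such as nausea, dizziness or headache (my examples) could begin in that interval and become worse once the drug is taken.

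A rule based only on start time cannot register that change. This matters more here than in many trials because AE reporting is the only post-dose safety measure visible in the plan: Protocol 12.2 relies on AE reporting, and vital signs are taken only at screening and baseline. Safety is part of the stated objective, and the endpoints in SAP 4.3 include treatment-emergent AEs, treatment-related AEs, and AEs by severity and relationship. If aggravated events fall outside those counts, the tables show new-onset events only and say nothing about aggravation by the drug.

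**Working it through.** The point rests on definitions, not on a power, alpha or sample size figure, so the plan has no number to reproduce. The check is to follow each kind of event through the rules as written.

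**Inputs.** The start-time definition (SAP 5.6.1, Protocol 14.8.1); the restriction of summaries to treatment-emergent AEs and its one exception (SAP 5.6.1); the causality sentence (Protocol 13.2.2); the rule for normal surgical consequences (Protocol 12.2); collection from consent (Protocol 13.3.1).

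**Pre-dose window after surgery.** At most 4.5 × 60 + 5 = 275 minutes from last stitch to dose. This is an upper limit, not a typical value.

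| Event | Where it appears |
|---|---|
| Starts at or after dosing | Treatment-emergent tables; also related tables if marked at least possibly related |
| Starts before dosing, does not worsen | Listing only, which is appropriate |
| Starts before dosing, serious or leads to discontinuation | SAE or discontinuation display, plus listing |
| Starts before dosing, non-serious, no discontinuation, severity rises after dosing, kept as one record with the original start | **Listing only** |
| Same event, worsening entered as a new record timed at the worsening | Treatment-emergent tables |
| Normal surgical consequence that worsens after dosing, dated from the worsening | Treatment-emergent tables |
| Same, dated from first symptom | **Listing only**, unless serious or leading to discontinuation |

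**Reading the fourth row.**
1. The start time precedes dosing, so the event fails the definition.
2. Summaries are limited to treatment-emergent AEs, so it is absent from the overall, system organ class, severity, demographic and 5% tables.
3. The related-event tables carry no exception. Even if the investigator marked the event as possibly related, it would not be counted there.
4. Protocol 13.2.2, applied to a record with a pre-dose time of occurrence, gives the investigator no basis for marking it as related.

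**What decides between rows four and five, and between six and seven.** Only the start time that the site enters. No section supplied says whether a worsening opens a new record or keeps the original onset. Two sites following the text could classify the same event differently.

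**Size.** The documents give neither an AE rate nor a count of events between surgery and dose. No estimate of the number affected can be derived from them.

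**The case against.** The strongest reply is that the gap may close in practice. Protocol 13.1.1 treats worsening as an AE in itself. Under Protocol 12.2 a normal surgical consequence is not an AE at all until it worsens after the drug, so the natural start is the time of worsening, which is post-dose. If sites work this way, the existing definition captures the event. CRF completion instructions may say so, but they are not among the documents supplied. The safeguards are also real: serious and discontinuation-causing events are tabulated whatever their start, and the rest are listed. The summaries are descriptive and no efficacy conclusion depends on them.

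Much of this stands, and it rules out several stronger readings that a reader might infer.

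- **That Protocol 12.2 contradicts the analysis rule.** It does not. The AE may be dated from the worsening, and no section says otherwise. The text is ambiguous, not inconsistent.
- **That Protocol 13.2.2 forbids linking any post-dose worsening to the drug.** It speaks of AEs occurring before first use and does not mention later worsening; the same section asks whether the product caused or contributed to an event. The bar applies to an event recorded with a pre-dose occurrence, not to a worsening recorded as its own event.
- **That safety data are lost.** They remain in the listing. The loss is from summary tables.
- **That enough events are missed to move a term across the 5% threshold.** With 150 per active arm the threshold is 0.05 × 150 = 7.5, so 8 subjects, but it applies to each preferred term. A count of subjects with any aggravated event cannot be compared with it, and the documents give no rate from which to form even that count.

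What the reply does not answer is the ordinary AE, not covered by Protocol 12.2, that is already recorded before dosing and keeps its original start. For that event the written rule gives exclusion, and nothing in the plan prevents it.

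**Conclusion.** The point holds within limits. As written, a non-serious AE that does not lead to discontinuation, is recorded with a start before dosing, and increases in severity afterwards would be listed but left out of the treatment-emergent, treatment-related, severity and 5% tables. For normal surgical consequences the outcome is undetermined, because it depends on an unstated recording convention.

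The conclusion assumes that the site keeps one record with the original onset. The documents neither require nor exclude that. The number of events affected is unknown. The effect is confined to the safety summaries; the primary and secondary efficacy analyses are untouched. The change is worth making because the rule itself omits aggravation, in a design where every subject passes through a post-surgical, pre-dose interval and AEs are the only visible post-dose safety measure.

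**What to change.** Make three changes, settled before database lock and release of the randomization codes:

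1. **SAP 5.6.1 and Protocol 14.8.1.** Define a treatment-emergent AE as one that starts at or after dosing, or that was present before dosing and increases in severity after it.
2. **Protocol 13.2.2.** Limit the sentence excluding a causal relationship to pre-dose events that did not worsen after dosing.
3. **Site instruction.** Enter a post-dose worsening as a new AE record with the time of worsening as its start and its own severity and causality assessment. Say that this includes the conditions covered by Protocol 12.2.

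The third change is needed for the first to work: no visible section asks for the time of a severity change, so a single record with one start time and one severity would not show it. The new record should not double-count subjects, since SAP 5.6.1 counts each subject once per term at the most severe event.

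The cost is a sentence or clause in each of the three sections, one completion instruction, a small added recording step at the site, and slightly higher treatment-emergent AE percentages. Alpha, sample size and the efficacy analyses do not change.

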### **5.6.2 Vital Signs**

Vital signs (temperature, pulse, respiratory rate, and blood pressure) collected at baseline will be summarised (number of subjects, mean, standard deviation, median, minimum and maximum) by treatment group.

## APPENDICES

### APPENDIX 1: SUMMARY TABLES AND FIGURES

The following tables and figures are planned for the Clinical Study Report. The numbering and titles of tables and figures in this document serves as guidance; the exact numbers and titles may be modified as appropriate.

Section / Table No	Title	Population / Analysis Sets
--------------------	-------	----------------------------

#### 14.1 Subject Disposition, Demographics, and Baseline Information

Table 14.1.1	Subjects Disposition and Analysis Sets	All Enrolled Subjects
Table 14.1.2	Summary of Protocol Deviations	All Randomized Subjects
Table 14.1.2.1	Summary of Major Protocol Deviations	All Randomized Subjects
Table 14.1.2.2	Summary of Minor Protocol Deviations	All Randomized Subjects
Table 14.1.3.1	Demographic and Baseline Characteristics	All Randomized Subjects
Table 14.1.3.2	Demographic and Baseline Characteristics	Safety Analysis Subjects
Table 14.1.3.3	Demographic and Baseline Characteristics	Per-Protocol Subjects
Table 14.1.4	Previous Medications	All Randomized Subjects
Table 14.1.5	Concomitant Medications	All Randomized Subjects
Table 14.1.5.1	Concomitant Medications Taken By $\geq$ 5% of Subjects in One or More Treatment Groups	All Randomized Subjects
Table 14.1.6	Vital Signs at Baseline	All Randomized Subjects

#### 14.2 Efficacy

Table 14.2.1	Kaplan-Meier Estimates of The Cumulative Percentage of Subjects with Confirmed Perceptible Pain Relief	All Randomized Subjects
Table 14.2.1.1	Kaplan-Meier Estimates of The Cumulative Percentage of Subjects with Confirmed Perceptible Pain Relief	Per-Protocol Subjects
Table 14.2.1.2	Kaplan-Meier Estimates of The Cumulative Percentage of Subjects with Confirmed Perceptible Pain Relief – Moderate Baseline Pain	All Randomized Subjects
Table 14.2.1.3	Kaplan-Meier Estimates of The Cumulative Percentage of Subjects with Confirmed Perceptible Pain Relief – Severe Baseline Pain	All Randomized Subjects
Table 14.2.1.4	Kaplan-Meier Estimates of The Cumulative Percentage of Subjects with Confirmed Perceptible Pain Relief – Male	All Randomized Subjects
Table 14.2.1.5	Kaplan-Meier Estimates of The Cumulative Percentage of Subjects with Confirmed Perceptible Pain Relief – Female	All Randomized Subjects
Table 14.2.1.6	Kaplan-Meier Estimates of The Cumulative Percentage of Subjects with Confirmed Perceptible Pain Relief – Age < 18 Years Old	All Randomized Subjects
Table 14.2.1.7	Kaplan-Meier Estimates of The Cumulative	All Randomized Subjects

	Percentage of Subjects with Confirmed Perceptible Pain Relief – Age >= 18 Years Old	
Table 14.2.1.8	Kaplan-Meier Estimates of The Cumulative Percentage of Subjects with Confirmed Perceptible Pain Relief – White Subjects	All Randomized Subjects
Table 14.2.1.9	Kaplan-Meier Estimates of The Cumulative Percentage of Subjects with Confirmed Perceptible Pain Relief – Non-White Subjects	All Randomized Subjects
Table 14.2.1.10	Kaplan-Meier Estimates of The Cumulative Percentage of Subjects with Confirmed Perceptible Pain Relief – Sensitivity Analysis 1	All Randomized Subjects
Table 14.2.1.11	Kaplan-Meier Estimates of The Cumulative Percentage of Subjects with Confirmed Perceptible Pain Relief – Sensitivity Analysis 2	All Randomized Subjects
Table 14.2.1.12	[REDACTED]	All Randomized Subjects
Table 14.2.2	[REDACTED]	All Randomized Subjects
Table 14.2.3	Percentage of Subjects with Confirmed Perceptible Pain Relief at Specified Times – Test NPX vs Placebo	All Randomized Subjects
Table 14.2.4	[REDACTED]	All Randomized Subjects
Table 14.2.5	[REDACTED]	All Randomized Subjects
Table 14.2.6	[REDACTED]	All Randomized Subjects
Table 14.2.7	[REDACTED]	All Randomized Subjects
Table 14.2.8	[REDACTED]	All Randomized Subjects
Table 14.2.9	[REDACTED]	All Randomized Subjects
Table 14.2.10	[REDACTED]	All Randomized Subjects
Table 14.2.11	[REDACTED]	All Randomized Subjects

**14.3 Safety**

Section / Table No	Title	Population / Analysis Sets
Table 14.3.1	Summary of Adverse Events	Safety Analysis Subjects
Table 14.3.2	Summary of Treatment-Emergent Adverse Events by System Organ Class and MedDRA Preferred Term	Safety Analysis Subjects
Table 14.3.3	Summary of Treatment-Emergent Adverse Events by Demographic Characteristics	Safety Analysis Subjects
Table 14.3.4	Summary of Treatment-Emergent Adverse Events by Severity	Safety Analysis Subjects
Table 14.3.5	Most Commonly Reported (>=5% of Subjects in	Safety Analysis Subjects

	One or More Treatment Groups) Treatment-Related Adverse Events	
Table 14.3.6	Summary of Treatment-Related Adverse Events	Safety Analysis Subjects
Table 14.3.7	Most Commonly Reported ( $\geq 5\%$ of Subjects in One or More Treatment Groups) Treatment-Related Adverse Events	Safety Analysis Subjects
Table 14.3.8	Summary of Treatment-Related Adverse Events By System Organ Class and MedDRA Preferred Term	Safety Analysis Subjects
Table 14.3.9	Summary of Treatment-Related Adverse Events By Severity	Safety Analysis Subjects
Table 14.3.10	Summary of Serious Adverse Events By System Organ Class and MedDRA Preferred Term	Safety Analysis Subjects
Table 14.3.11	Summary of Withdrawals Due to Adverse Events By System Organ Class and MedDRA Preferred Term	Safety Analysis Subjects

**FIGURES:**

Figure 14.1	Kaplan-Meier Estimates of the Cumulative Percentage of Subjects with Confirmed Perceptible Pain Relief	All Randomized Subjects
Figure 14.1.1	Kaplan-Meier Estimates of the Cumulative Percentage of Subjects with Confirmed Perceptible Pain Relief – Moderate Baseline Pain	All Randomized Subjects
Figure 14.1.2	Kaplan-Meier Estimates of the Cumulative Percentage of Subjects with Confirmed Perceptible Pain Relief – Severe Baseline Pain	All Randomized Subjects
Figure 14.1.3	Kaplan-Meier Estimates of the Cumulative Percentage of Subjects with Confirmed Perceptible Pain Relief – Male	All Randomized Subjects
Figure 14.1.4	Kaplan-Meier Estimates of the Cumulative Percentage of Subjects with Confirmed Perceptible Pain Relief – Female	All Randomized Subjects
Figure 14.1.5	Kaplan-Meier Estimates of the Cumulative Percentage of Subjects with Confirmed Perceptible Pain Relief – Age < 18 Years Old	All Randomized Subjects
Figure 14.1.6	Kaplan-Meier Estimates of the Cumulative Percentage of Subjects with Confirmed Perceptible Pain Relief – Age $\geq$ 18 Years Old	All Randomized Subjects
Figure 14.1.7	Kaplan-Meier Estimates of the Cumulative Percentage of Subjects with Confirmed Perceptible Pain Relief – White Subjects	All Randomized Subjects
Figure 14.1.8	Kaplan-Meier Estimates of the Cumulative Percentage of Subjects with Confirmed Perceptible Pain Relief – Non-White Subjects	All Randomized Subjects
Figure 14.2	[REDACTED]	All Randomized Subjects

Figure 14.3	[REDACTED]	All Randomized Subjects
Figure 14.4	[REDACTED] t	All Randomized Subjects
Figure 14.5	[REDACTED]	All Randomized Subjects
Figure 14.6	[REDACTED]	All Randomized Subjects
Figure 14.7	[REDACTED]	All Randomized Subjects

## APPENDIX 2: DATA LISTINGS

The following listings are planned for Clinical Study Report. The numbering and titles of data listings in this document serve as guidance; the exact numbers and titles may be modified as appropriate.

Listing No.	Title	Population
16.1.7	Randomization Schedule	All Randomized
16.2.1	Subject Disposition	All Randomized
16.2.2.1	Discontinued Subjects	All Randomized
16.2.2.2	Subjects with Protocol Deviations	All Randomized
16.2.2.3	Subjects Excluded from Per Protocol Population	All Randomized
16.2.3.1	Demographic and Baseline Characteristics	All Randomized
16.2.3.2	Significant Medical History	All Randomized
16.2.3.3	Previous and Concomitant Medications	All Randomized
16.2.3.4	Non-Drug Therapy/Procedure	All Randomized
16.2.4.1	Surgery Information and Baseline Pain Measurement	All Randomized
16.2.4.2	Tooth Extractions	All Randomized
16.2.4.3	Dosing Time of Study Medication	All Randomized
16.2.5.1	[REDACTED]	All Randomized
16.2.5.2	[REDACTED]	All Randomized
16.2.5.3	[REDACTED]	All Randomized
16.2.5.4	[REDACTED]	All Randomized
16.2.6.1	Subjects with Treatment-Emergent Adverse Events	All Randomized
16.2.6.2	Subjects with Non-Treatment-Emergent Adverse Events	All Randomized
16.2.6.3	Subjects with Adverse Events that Resulted in Study Discontinuation	All Randomized
16.2.6.4	Subjects with Serious Adverse Events	All Randomized
16.2.6.5	MedDRA Preferred Terms for Adverse Events	All Randomized
16.2.6.6	Self-Reported Pregnancy	All Randomized
16.2.6.7	Vital Signs	All Randomized
16.2.7	Follow-up Interview	All Randomized

